Our goal will be to enroll 60 patients diagnosed with PNES, with 30 randomized to the treatment arm (motivational interview) and 30 randomized to the control arm (informational interview).

Potential subjects will be asked if they are willing to meet with study staff by a member of the clinical team during their inpatient admission. If the patient is willing, they will be approached during their admission by a member of the study staff. The recruiter will not be a member of the treatment team, and in all cases the recruiter will clearly specify that the patient will receive the same standard-of-care treatment for PNES (initial clinical follow-up with neuropsychiatrist and epileptologist and psychotherapy from a licensed therapist) whether or not they participate in the study.

The purpose and structure of the study will be described, and if the individual is interested than the full informed consent process will completed, including detailed review of all potential risks and benefits- Because the informed consent process will be completed during an inpatient admission, time constraints will be minimized and the patient will have ample time to consider his or her consent. If informed consent is obtained, then study procedures will begin.

Baseline demographic data, psychiatric comorbidities, quality of life, and healthcare resource utilization will be recorded in the EMU and the patient will be randomized to treatment (standard treatment + motivational interviewing) vs. control (standard treatment only). The patient will be scheduled for an initial appointment in the “long-term monitoring clinic” with an epileptologist and a neuropsychiatrist (part of standard care for PNES at BWH). At the end of this clinic appointment the patient will have either a motivational interview (treatment) or informational interview (control) depending on their randomization. They will then be referred for weekly psychotherapy either at BWH or with a local provider (again, part of standard care for PNES at BWH). After 4 months they will be called and have a phone interview regarding their adherence to treatment, their reasons for adherence or non-adherence, seizure frequency, quality of life, and healthcare resource utilization over the prior 3 months.

Briefly describe study procedures. Include any local site restrictions, for example, “Subjects enrolled at Partners will not participate in the pharmacokinetic portion of the study.” Describe study endpoints.

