Baseline demographic data, psychiatric comorbidities, seizure frequency, quality of life, and healthcare resource utilization will be recorded following enrollment during the inpatient stay as part of PHRC IRB protocol 2013P000133. If the patient is not enrolled in protocol 2013P000133, baseline demographic data, seizure data, psychiatric comorbidities, qualities of life and healthcare resource utilization will be collected during the admission at which the patient is diagnosed, as detailed in appendix 1. All enrolled subjects will be scheduled for an initial appointment in the joint psychiatry-neurology clinic with a board certified neuropsychiatrist and board certified neurologists, which is standard of care for newly diagnosed PNES patients at Brigham and Women’s Hospital.

All subjects will attend the initial clinic visit with the neuropsychiatrist and epileptologist. At the end of this visit, those subjects randomized to motivational interviewing will be questioned using standardized motivational interviewing techniques by the study author who is a board certified neurologist and who will have formal training and certification in motivational interviewing. Motivational interviews will include the classical 4 steps of MI: 1) engagement (in which the patient’s goals and interests are elicited and the therapeutic alliance is established); 2) focusing (in which the specific subjects of discussion and intervention are negotiated); 3) strengthening motivation (in which the patients’ reasons for healthcare intervention are made explicit, discussed, and reinforced); and 4) planning (in which actions for healthcare intervention are planned out based on the patients’ own goals and interests).

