The initial clinic visit and subsequent interview will be recorded with the patients’ consent, and blinded reviewers hired through the department of psychiatry, trained and certified in motivational interviewing, will score the audio recordings using the Motivational Interviewing Treatment Integrity code (MITI) 4.0 to assess fidelity to standardized motivational interviewing techniques. Recordings and blinded review of interviews are for the sole purpose of ensuring that the interviewer is in fact using proper interviewing techniques (ie motivational interviewing techniques for patients in the motivational interviewing arm and abstinence from motivational interviewing techniques in the control arm). Such recordings and review are recommended in motivational interviewing research.

Those subjects randomized to the control group will also undergo an initial clinic visit with a neuropsychiatrist and neurologists – again recorded with the subjects’ consent and scored using the MITI 4.0 to assess abstinence from motivational interviewing techniques. However they will not undergo any subsequent motivational interview. Following the initial clinic visit, all subjects with ongoing seizures will either be scheduled for ongoing psychotherapy for treatment of PNES at Brigham and Women’s Hospital or referred to a local psychotherapist according to their preference.

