All subjects will be contacted by phone at 4 month follow-up. If necessary they will be called 5 times at various times during the day and early evening. If they are not reached, they will receive a letter requesting them to contact the study staff to complete the study. Subjects will be questioned about their adherence to treatment. The primary outcome will be the number of psychotherapy sessions for the treatment of PNES in which they have participated over the past three months. They will also be assessed for secondary outcomes including dichotomous adherence (either seizure freedom or active participation in psychotherapy for the treatment of PNES, with more than 5 sessions over the past 3 months), seizure frequency over the past month, number of hospitalizations and emergency department visits over the past 3 months, and quality of life as measured by the brief QOLIE-10 instrument. For those patients who give permission, their psychotherapists will be contacted by study staff to confirm the exact number of psychotherapy sessions over the past 3 months. A standard Partners clinical records release form with the patient’s signature will be sent to the therapist’s office.

Biostatistical Analysis:

A) Motivational Interviewing Treatment Integrity

Fidelity to motivational interviewing techniques during motivational interviewing sessions (intervention arm) will be assessed by blinded reviewers using the Motivational Interviewing Treatment Integrity code (MITI) 4.0. Relational scores and technical scores of ≥ 4 will be taken as indicating adherence to motivational interviewing techniques. Conversely abstinence from motivational interviewing techniques during informational interviews (control arm) will also be assessed by blinded reviewers using the MITI 4.0. Relational scores and technical scores of ≤ 2 will be taken as indicating abstinence from motivational interviewing techniques.

B) Outcome data

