Outcome data collected during study, collected at 4 month follow-up, includes seizure frequency over the past 3 months, number of emergency department visits over the past 3 months, QOLIE-10 score (see attached instrument), and participation in psychotherapy for the treatment of PNES (and number of sessions over the past 3 months). The primary outcome will be adherence, defined as attending 8 or more psychotherapy sessions over the past 3 months. Secondary outcomes will include decrease in PNES frequency, seizure freedom, change in QOLIE-10 score, and change in monthly ED visits.

Intergroup comparisons will be made between the treatment arm (motivational interviewing) and control arm (informational interviewing) using the t-test or Wilcoxon rank-sum test depending on normality of distributions.

C) Power analysis:

Sample size of 30-per-arm was calculated to detect a difference in adherence of 25% vs. 60% with power of 0.80 and alpha of 0.05.

For studies involving treatment or diagnosis, provide information about standard of care at Partners (e.g., BWH, MGH) and indicate how the study procedures differ from standard care. Provide information on available alternative treatments, procedures, or methods of diagnosis.

All patients enrolled in study will still receive standard of care for patients diagnosed with PNES at Brigham and Women's Hospital: initial clinical follow-up with neuropsychiatrist and epileptologist and psychotherapy from a licensed therapist. Study patients will additionally receive either an informational interview (control arm) or a motivational interview (treatment arm) following their initial clinic follow-up.

Describe how risks to subjects are minimized, for example, by using procedures which are consistent with sound research design and which do not unnecessarily expose subjects to risk or by using procedures already being performed on the subject for diagnostic or treatment purposes.

Research procedures (motivational interviewing vs. informational interview) are consistent with sound research design. Motivational interviewing has been studied and used for years in promoting abstinence from substance abuse and adherence with treatment in other disorders (HIV, schizophrenia, etc.), and is thought to be associated with minimal risk.

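### The primary outcome rests on a 4-month phone self-report; the attendance record should be the primary source in both arms, sought whether or not the call succeeds

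*Combined protocol and SAP*

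**What the plan says.** All of this is in the combined protocol and SAP.

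- **Outcome.** The follow-up paragraph of Research Design and Methods says "The primary outcome will be the number of psychotherapy sessions for the treatment of PNES in which they have participated", counted over three months. Biostatistical Analysis, B) Outcome data, says "The primary outcome will be adherence, defined as attending 8 or more psychotherapy sessions over the past 3 months". The two definitions must be reconciled, but both are counts of attendance and this point applies to either.
- **Source.** Research Design and Methods says "After 4 months they will be called and have a phone interview regarding their adherence to treatment". The therapist is a second source, by permission: "For those patients who give permission, their psychotherapists will be contacted by study staff to confirm the exact number of psychotherapy sessions". A signed release form is to be sent to the therapist's office.
- **Unreached patients.** Up to five calls at varied times are planned. After that, "If they are not reached, they will receive a letter requesting them to contact the study staff to complete the study".
- **Analysis.** Section B compares the arms "using the t-test or Wilcoxon rank-sum test depending on normality of distributions". It gives no order of precedence between sources, no analysis set and no missing-data rule. Data and Safety Monitoring adds only that reasons for leaving are documented.
- **Who has a therapist.** After the clinic visit "all subjects with ongoing seizures will either be scheduled for ongoing psychotherapy for treatment of PNES", at the hospital or with a local therapist. Patients whose seizures have stopped are not covered by that sentence.
- **Blinding.** It is described only for the reviewers who score the audio recordings. The person who makes the follow-up calls is not identified.

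**The concern.** The trial tests an intervention meant to make patients attend therapy, and it measures attendance by asking them. Two problems follow from the procedure as written.

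First, self-reported attendance can be overstated. Equal overstatement in both arms shrinks a true difference and costs power. Unequal overstatement shifts the result towards the arm that overstates more. The therapist's count would correct this, but only where permission is given, and the plan does not say that the therapist's figure replaces the patient's when they differ.

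Second, the outcome depends on reaching the patient. People who do not attend therapy may also be harder to reach by phone (an inference), so missingness may be tied to the outcome itself. A clinic or therapist may hold the answer for some of these patients, but the plan does not direct staff to look for it when the calls and the letter fail. With 30 per arm and no stated allowance for loss, the choice of how to treat such patients could decide the result, and it could be made after the data are seen.

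**Working it through.** **Inputs from the documents.** 30 per arm; 25% vs 60% adherence; power 0.80; alpha 0.05 (taken as two-sided); primary threshold of 8 or more sessions. All over-reporting, correction and loss rates below are assumptions.

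**1. The plan's own figure.** Pooled normal approximation, mean rate 0.425:
n = [1.96 × √(2 × 0.425 × 0.575) + 0.842 × √(0.25 × 0.75 + 0.60 × 0.40)]² / 0.35² = 30.1, so 31 per arm. The arcsine formula gives 30. Exact power of the uncorrected chi-square test at 30 per arm is 0.802. The stated 30 is reproduced, with nothing spare for loss or misclassification.

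Steps 2, 4 and 5 use exact binomial enumeration of that test for power and false-positive rates. At 30 per arm the t-test and Wilcoxon test applied to the 0/1 outcome give the same values.

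**2. Over-reporting.** If a share r of non-adherers is recorded as adherent, the observed rate is p + (1 − p)r.

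| Case | Control | MI | Result |
|---|---|---|---|
| True 25% vs 60%, r = 0 | 25% | 60% | power 0.80 |
| r = 20% in both arms | 0.25 + 0.75 × 0.20 = 40% | 0.60 + 0.40 × 0.20 = 68% | power 0.60 |
| Same, half corrected by therapists | 32.5% | 64% | power 0.71 |
| No effect, 25% each, r = 0 | 25% | 25% | 2.5% favouring MI |
| No effect, r = 10% control, 20% MI | 32.5% | 40% | 8.4% favouring MI |
| Same, half corrected | 28.75% | 32.5% | 4.8% favouring MI |

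For the session count, a simulation gave 6% favouring MI in the 10%/20% case, against about 2.5% with no over-reporting. It assumed 0 to 13 sessions, 35% never starting, 25% at 8 to 13, the rest at 1 to 7, and over-reporters saying 8.

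**3. How much the missing rule matters.** Suppose reached patients show 25% vs 60% and 6 of 30 per arm are unreached, so 24 are reached, with expected adherers 6 and 14.4.
- Complete cases: 35 points.
- Unreached counted as non-adherent: 6/30 = 20% vs 14.4/30 = 48%, or 28 points.
- Extremes: 14.4/30 − 12/30 = 8 points, and 20.4/30 − 6/30 = 48 points.

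**4. Loss tied to non-adherence, complete cases.** If the same share s of non-adherers is lost in each arm, the observed rates are 0.25/(1 − 0.75s) and 0.60/(1 − 0.40s). For s = 10%, 20%, 30%, 40%, 50% and 60% the differences are 0.355, 0.358, 0.359, 0.357, 0.350 and 0.335. The true difference is 0.35, so there is almost no distortion.

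**5. Price of counting missing as non-adherent.**
- 20% lost at random in each arm: 20% vs 48%, power 0.64. Complete cases (24 per arm, 25% vs 60%) give 0.73.
- No effect, 10% vs 30% lost at random: 22.5% vs 17.5%, giving 6.8% false positives for the arm with less loss. Complete cases (27 vs 21, both 25%) give about 2.2%.

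**The case against.** The strongest case is that the plan already does much of this. Repeated calls, a letter, a signed release and contact with therapists are all there. Asking therapists to confirm an exact number suggests that their count is meant to prevail. The permission clause does not limit who is asked or when; it may already mean everyone, and the consent pages are not in the copy reviewed. On that reading only a few sentences of analysis rules are missing. This stands in part, and it is why the fix is cheap. It does not remove the point: confirmation is not the same as being the primary source, and no text directs staff to seek a record for a patient who could not be reached.

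Three stronger readings are tempting, and the documents do not support them.

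- *The result will be biased towards motivational interviewing.* The false-positive figures need unequal over-reporting, which no passage establishes. Expected Benefits says both arms get extra neurologist time, and the standard-of-care paragraph gives controls an informational interview. Research Design and Methods in one place describes control as standard care alone, and in another describes only the clinic visit for controls. These passages must be reconciled. Until then it cannot be settled whether equal or unequal over-reporting is more plausible.
- *Equal loss in both arms inflates the effect.* Losing 20% of each whole arm, all of them non-adherers, would give 0.25/0.80 = 31% vs 0.60/0.80 = 75%, a difference of 0.44. But that means losing 0.20/0.75 = 27% of control non-adherers and 0.20/0.40 = 50% of those in the motivational-interview arm. With equal shares lost, the difference stays at about 0.34 to 0.36.
- *The caller is unblinded.* The interview in the active arm is done by the study author (patients are "questioned using standardized motivational interviewing techniques by the study author who is a board certified neurologist"), but nobody is named as the caller. The text is silent, and silence is not evidence of unblinding.

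It is also fair that a record can be sought only if the therapist is known. That is hardest for unreached patients who were referred locally.

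**Conclusion.** The point holds as a design weakness that is cheap to repair, not as a demonstrated bias. It is certain from the text that the primary outcome comes from a phone self-report, that the therapist's count is sought only by permission, and that no rule covers disagreement between sources or patients who are never reached. A better source is already within the plan's reach.

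The size is uncertain because every rate used is assumed. The calculations show sensitivity only: a drop in power of up to 0.20 under equal 20% over-reporting, and a rise in one-direction false positives of about 6 percentage points in the assumed 10%/20% case, or about 2 points if therapists correct half. An unwritten missing-data rule can move an observed difference by several points at 20% loss. The change should be made, though the trial does not stand or fall by it. Confidence in the practical size is medium.

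**What to change.** 1. Ask every patient in both arms for the voluntary records release at enrolment or at the clinic visit, adding the therapist's name after referral. Patients who decline stay in the study.
2. State that the therapist or clinic attendance record is the primary source in both arms, sought whether or not the call succeeds. Use self-report only where no record can be obtained.
3. Score as zero sessions those whom records or their own report show never started therapy. This includes patients not referred because their seizures had stopped; the dichotomous secondary outcome already gives credit for seizure freedom.
4. State one primary rule, the same in both arms, for patients with neither source. Counting them as non-adherent is one option, but it does worse than complete cases under random loss, so the choice should be justified in advance.
5. Add sensitivity analyses by source, on complete cases, and under the opposite assumption for missing patients.

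Optional, and not needed for the above: have an existing staff member who is not told the arm make the calls. The documents do not show how many staff there are, so this may cost some time.

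**Cost.** The release form and therapist contact are already planned, so the additions are an earlier request, somewhat more therapist contacts and a short analysis paragraph. Self-report or missing data will remain where release is declined, the therapist is unknown, or the therapist does not reply.

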**PARTNERS HUMAN RESEARCH COMMITTEE
PROTOCOL SUMMARY**

Answer all questions accurately and completely in order to provide the PHRC with the relevant information to assess the risk-benefit ratio for the study. Do not leave sections blank.

PRINCIPAL/OVERALL INVESTIGATOR

[name]

PROTOCOL TITLE

Motivational interviewing to enhance adherence of patients with psychogenic non-epileptic seizures: a model of patient engagement in functional neurological symptom disorders

FUNDING

Practice Research Training Fellowship (American Academy of Neurology, American Brain Foundation)

VERSION DATE

July 8th, 2015

SPECIFIC AIMS

Concisely state the objectives of the study and the hypothesis being tested.

NB: Specific Aims 1 and 2 pertain to the first part of this project, detailed under BWH IRB protocol 2013P000133. Specific Aim 3 pertains to the second part of this project, detailed here.

Aim 1: To identify the baseline characteristics which correlate most closely with non-adherence to treatment in patients with PNES.

Hypothesis 1: Factors including low income, low educational achievement, unmarried status, lack of access to transportation, presence of psychiatric comorbidities, high seizure frequency, and long duration since onset of PNES will correlate with non-adherence in patients with PNES.

Aim 2: To identify the factors to which non-adherent patients with PNES attribute lack of adherence.

Hypothesis 2: Patients will most frequently attribute their lack of adherence to external factors including ineffective treatment, lack of empathy on the part of their physicians, and difficulty arranging transportation or time away from work/childcare. Patients will not attribute non-adherence to internal factors such as ambivalence about treatment, avoidance, help-rejection, or psychiatric comorbidities.

Aim 3: To determine whether motivational interviewing improves adherence to treatment (primary outcome), seizure frequency, healthcare usage, and quality of life (secondary outcomes).

Hypothesis 3: A brief in-person interview, using motivational interviewing techniques, will improve adherence, seizure frequency, healthcare usage, and quality of life at 4-month follow-up among patients with PNES when compared to a control group receiving only informational interviewing.

BACKGROUND AND SIGNIFICANCE

Provide a brief paragraph summarizing prior experience important for understanding the proposed study and procedures.

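### The planned unadjusted comparison of the primary adherence outcome is valid, but prespecified adjustment for two baseline factors would be a cheap improvement at 30 per arm

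*Combined protocol and SAP*

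**What the plan says.** The only between-arm analysis is in Biostatistical Analysis, B) Outcome data: "Intergroup comparisons will be made between the treatment arm (motivational interviewing) and control arm (informational interviewing) using the t-test or Wilcoxon rank-sum test", chosen by normality. No covariate is named. The places that mention randomisation (Research Design and Methods, Recruitment Procedures, Consent Procedures) describe no stratification, blocking or minimisation.

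Hypothesis 1 under Specific Aims expects that "presence of psychiatric comorbidities, high seizure frequency, and long duration since onset of PNES will correlate with non-adherence in patients with PNES", alongside four social factors (income, education, marital status, transport). It belongs to Aim 1, which the document assigns to the companion protocol.

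On baseline data, the study procedures in Research Design and Methods say: "Baseline demographic data, psychiatric comorbidities, seizure frequency, quality of life, and healthcare resource utilization will be recorded following enrollment". That sentence covers patients who are also in the companion protocol. For the others the same section provides for the same categories, with seizure data in place of seizure frequency, and refers to appendix 1 for detail.

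The primary outcome is given twice. Section B has "The primary outcome will be adherence, defined as attending 8 or more psychotherapy sessions over the past 3 months". The follow-up paragraph just before the Biostatistical Analysis has "The primary outcome will be the number of psychotherapy sessions for the treatment of PNES". The power paragraph reads: "Sample size of 30-per-arm was calculated to detect a difference in adherence of 25% vs. 60% with power of 0.80 and alpha of 0.05".

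**The concern.** Neither the design nor the analysis uses baseline information on the primary outcome, although the investigators have said which characteristics they expect to go with it and plan to collect at least two of them. At 30 per arm, simple randomisation can leave a visible imbalance in such a factor. If it does, the plan has no prespecified answer, and an adjustment chosen after the data are seen is easy to discount. The design is sized at 0.80 power with no stated reserve, so a few points of power are worth having if they cost almost nothing.

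**Working it through.** **Inputs.** From the power paragraph: 30 per arm, 25% vs 60%, alpha 0.05 (taken as two-sided, since that reproduces the plan). Assumed, because the documents give neither: the share of outcome variance explained by the covariates (R2) and the prevalence of a yes/no factor.

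**1. The plan's own figure.** Pooled rate = (0.25 + 0.60)/2 = 0.425.
- SE under the null = sqrt(2 × 0.425 × 0.575 / 30) = 0.1276.
- SE under the alternative = sqrt((0.25 × 0.75 + 0.60 × 0.40)/30) = sqrt(0.4275/30) = 0.1194.
- Power = Φ((0.35 − 1.96 × 0.1276)/0.1194) = Φ(0.836) = 79.9%.
- The same formula solved for 80% gives 31 per arm. Exact power of the t-test on the 0/1 outcome at 30 per arm is 80.2%.

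The stated sample size reproduces and does not depend on adjustment.

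**2. Power with adjustment.** Approximate variance factor for k covariates: f = (1 − R2) × (1 + k/(60 − k − 3)). With k = 2 the second term is 1 + 2/55 = 1.036. Both standard errors above are multiplied by sqrt(f).

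| R2 (assumed) | f | Power, 2 covariates | Change from 79.9% |
|---|---|---|---|
| 0 | 1.036 | 78.4% | −1.5 |
| 0.05 | 0.985 | 80.5% | +0.6 |
| 0.10 | 0.933 | 82.6% | +2.7 |
| 0.20 | 0.829 | 87.0% | +7.1 |
| 0.30 | 0.725 | 91.1% | +11.2 |

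Entering all seven factors of Hypothesis 1 would give 74.2% at R2 = 0 and 78.8% at R2 = 0.10, so it costs power unless R2 exceeds about 0.12. Only about 0.425 × 60 = 25.5 adherent patients are expected, which also argues for a short list.

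**3. Simulation check.** Binary outcome, linear model, one 50:50 factor and one continuous factor, marginal rates held at 25% and 60%. Across two independent runs, unadjusted power was 0.80 to 0.81. Adjusted power was:
- 0.81 to 0.82 with odds ratios of 0.5 and 0.7 per SD;
- 0.825 to 0.835 with 0.33 and 0.6;
- 0.86 with 0.25 and 0.5;
- about 0.79 with useless covariates.

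Type I error of the adjusted linear model stayed near 5%. A logistic likelihood-ratio test ran slightly high under the null (0.055 to 0.06), which favours the linear or standardised form.

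**4. Chance imbalance.** Probability that a yes/no factor differs by 20 points or more (6 or more patients of 30) between arms, from two independent binomials: 15.5% at 50% prevalence, 12.0% at 30% or 70%, 7.5% at 80%, 1.8% at 90%.

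**5. What such an imbalance does.** Shift in the arm difference = 0.20 × (difference in adherence across the factor). For a 50:50 factor and 40% adherence overall (assumed):
- odds ratio 0.5: 48.2% vs 31.8%, shift 0.20 × 16.5 = 3.3 points;
- odds ratio 0.33: 52.9% vs 27.1%, shift 0.20 × 25.9 = 5.2 points;
- odds ratio 0.25: 55.9% vs 24.1%, shift 0.20 × 31.8 = 6.4 points.

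The planned difference is 35 points.

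**The case against.** The strongest reply is that nothing is broken. Randomisation makes the unadjusted comparison valid, and chance imbalance is already counted in its 5% error rate and its 0.80 power. That stands in full. A reader might infer that the plan is biased or its sample size wrong; the documents support neither.

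Second, the gain may be nil. Hypothesis 1 is an untested statement of correlation from the companion protocol. It is not a claim that these factors cause non-adherence, and no strength of association is given. That also stands, so precision is only possibly forgone.

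Third, a reader might infer that all seven hypothesised predictors are recorded in everyone. Only psychiatric comorbidities and seizure frequency or seizure data are itemised. The rest may lie within demographic data or appendix 1, which is not in the text available. The first baseline list in Research Design and Methods also omits seizure frequency. So baseline PNES frequency in every subject is a fair inference, not a certainty.

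Fourth, a larger distortion is easy to construct. Adherence of 20% vs 60% across a factor would turn a 20-point imbalance into an 8-point shift. That is an odds ratio of 1/6, stronger than any scenario simulated here, and nothing in the documents supports it. Likewise 15.5% is the highest of the prevalences shown; a comorbidity present in nearly everyone would rarely be imbalanced and would carry little information.

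What the reply does not remove is the asymmetry: a loss of at most about 1.5 points against a gain of several if the investigators' own hypothesis is even moderately right.

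**Conclusion.** The point holds as an efficiency and chance-imbalance improvement, not as a correction of an error. For two prespecified covariates the change in power runs from about −1.5 to −1 points (useless) through about +1 or less (weak) to +3 at R2 = 0.10 and +7 at R2 = 0.20, with type I error near 5%. These figures rest on an assumed R2 and on the binary form of the outcome; the count form was not simulated. The simulations used ordinary model-based standard errors. The imbalance figures assume simple randomisation and the stated prevalences.

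**What to change.** First settle whether the primary outcome is the session count or the 8-session threshold; no adjusted model can be fixed until then. Then state in section B:

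- The primary model contains arm, log(1 + baseline PNES frequency) and psychiatric comorbidity (yes/no).
- For the binary outcome, report the adjusted risk difference (linear model with robust standard error, or standardised) with a 95% CI.
- For the count, use a linear model of sessions with the same covariates and robust standard errors, and report the adjusted mean difference with a 95% CI.
- The covariates are fixed now and not chosen from Aim 1 results, because the plan expects most eligible patients to be in both protocols.
- The unadjusted comparison is kept as a sensitivity analysis.

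Confirm that appendix 1 captures PNES frequency for patients outside the companion protocol, separately from epileptic seizures, since patients with both diagnoses are eligible. If comorbidity proves to be nearly universal, a more informative coding should be fixed before outcome data are seen.

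Cost: one paragraph and, if appendix 1 holds the item, no new data. The downside is two model degrees of freedom, about 1 to 1.5 points of power if neither factor predicts adherence.
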